### Recruitment of CAB-LA Users

For the survey component of the study, CAB-LA users will be recruited using recruitment flyers/posters with a quick response (QR) code linked to the survey, displayed at different clinical settings where they access PrEP (for example, but not limited to hospitals, outpatient clinics, and pharmacies) across Canada. In addition, HCPs participating in the HCP survey may also direct CAB-LA users to the QR code for the survey. To reach target sample sizes and to ensure representativeness of the user sample, recruitment may additionally be conducted through Mediscys. Recruitment of CAB-LA users will be conducted in geographic regions where CAB-LA is publicly listed. As access expands across Canada, recruitment will also be expanded to ensure representation from all possible regions. The data will be analyzed by geographical location, with some regions anticipated to be grouped together based on available sample size (e.g., Western Canada). Recruitment and survey materials for the secondary objectives will not contain language suggesting that the study was requested by HC.

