### Logistics and Monitoring

Individuals who are interested in participating will be directed to a brief screening questionnaire to assess eligibility for survey participation against study inclusion criteria. If the individual is identified as eligible to participate in the survey based on screener responses, they will be directed to an electronic version of the consent form. Once they have electronically indicated their consent to participate (selecting a consent statement and providing an electronic signature), they will subsequently be directed to complete the survey. Based on personal information collected during the screening and consent process, including participant name and email address, a check will be performed to ensure that there is no prior completion of the same survey in the system using the same name and email entered. The purpose of this check is to prevent participants from completing the same survey multiple times. To help optimize response rates, up to two reminder emails will be sent to individuals who have not completed the survey (one after 7 days and another after 14 days). To promote further education, correct responses to the survey questions, where applicable, will be displayed immediately after submission of the survey (before a participant has exited the survey) in a PDF file. A link to the aRMMs will be included in the PDF and on the online survey platform for future reference.

For each survey, a live dashboard will be set up to monitor recruitment progress against targets, allowing for adjustments to the recruitment strategy to be made in real time, as needed (e.g., increase the number of recruitment sites and/or target recruitment of certain participant groups to improve representativeness).

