HCPs will receive a one-time payment of \$350 upon completing the survey, while CAB-LA users will receive \$100. For the pilot testing, each of the 5 HCPs will be compensated \$350, and each of the 5 community members will receive \$100. Remuneration details will be provided in the consent form. For both surveys, unique survey links will be generated for each participant. The unique link will enable participants to save their progress and return to complete the survey at a later time, minimizing potential incomplete responses. In addition, checks will be in place to ensure that each link can only be used once to complete the survey and receive payment. Checks may include a combination of the following: 1) checking IP addresses; 2) checking for duplicate email addresses for payment; 3) checking for suspicious email addresses; 4) running PercentMatch statistical function assess the level of identical observations in the survey dataset; 5) checking for realistic survey completion times. Recruitment will continue for approximately five months, unless the closing criterion is met. The closing criterion for the survey is reaching the maximum sample size of 100 HCPs and 250 CAB-LA users.

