## 7.9. Limitations of the Research Methods

This study is subject to several limitations. Firstly, there is the potential for selection bias, given the voluntary nature of participation in the survey study, for both HCPs and CAB-LA users. Additionally, although efforts will be made to recruit a representative sample of different types of HCPs and CAB-LA users from different settings, the sample included in the study may not be representative of all HCPs and CAB-LA users. Further, given the self-reported nature of the data within this study, there are a number of additional biases to consider. First, self-reported data may be subject to reporting bias; second, recall bias may play a role in accurately remembering information, for example for questions related to CAB-LA user behaviours. Furthermore, given that the correct answers to the questions assessing knowledge can be identified by referring to the aRMMs, the consent form and survey instructions will clearly state that the intent of the survey is to assess general levels of knowledge and awareness, and that participants' responses cannot be linked back to them, in order to encourage participants to respond based on their own knowledge without referring to other materials. Lastly, CAB-LA users within the PSP may have important differences from those who are not in the PSP, therefore, the data may not be generalizable to all individuals who would receive CAB-LA. CCI

CCI

CCI

CCI

All limitations mentioned in this section will be included in the final study reports.

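### Correct answers are shown at submission while the same survey is still recruiting, so the knowledge success rate may be biased upward by an unknown amount

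*Protocol*

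**What the plan says.** Under Logistics and Monitoring in section 7.5.2, the protocol states that "correct responses to the survey questions, where applicable, will be displayed immediately after submission of the survey", in a PDF shown before the respondent leaves the survey. The stated purpose is educational. It adds: "A link to the aRMMs will be included in the PDF and on the online survey platform for future reference". The same section says "Recruitment will continue for approximately five months, unless the closing criterion is met". That criterion is 100 HCPs and 250 users.

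Users are reached by posters with a QR code, "displayed at different clinical settings where they access PrEP", and "HCPs participating in the HCP survey may also direct CAB-LA users to the QR code for the survey". A recruitment vendor may be used for both groups.

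Section 7.3.2 (Assessment of success) sets the criterion. A respondent succeeds in a domain with at least 80% of its questions answered correctly or appropriately, and the population target is at least 70% of respondents succeeding. Knowledge and behaviour are scored separately.

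Section 7.9 accepts that the knowledge answers can be looked up in the aRMMs. Its remedy is wording in the consent form and survey instructions, intended "to encourage participants to respond based on their own knowledge without referring to other materials".

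**The concern.** From the first online submission onward, someone outside the study team has seen the item-by-item answers to a survey that other people have yet to take. Section 7.9 treats answering from a source as a threat to the knowledge measure, yet section 7.5.2 opens a more direct route to it than the one that 7.9 discusses.

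The two routes differ in kind. Reading an aRMM is exposure to the measure under evaluation. Reading an answer list is not, and it can produce a passing score without the aRMM having had any effect.

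The direction matters because success is judged in one direction only, and seeing correct answers can only raise a knowledge score. The assessment is planned once and reported to Health Canada. Section 7.10 ties the search for gaps, and the corrective action, to thresholds not being reached. A pass produced in part by circulated answers would leave that step untriggered.

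**Working it through.** **1. Do the described checks cover this route?**

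- Name and email check (7.5.2): prevents one person from completing the same survey twice.
- Single-use links, IP addresses, duplicate or suspicious emails, PercentMatch and completion times (7.5.2): aimed at repeat or fraudulent entry. PercentMatch and timing might flag some copied answers, but are not described for that purpose.
- Sensitivity analysis (7.7): excludes inconsistent or implausibly fast respondents.
- Instruction (7.9): asks respondents not to consult other materials.

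None is aimed at one person passing answers to another, and no delay of the PDF is described.

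**2. The plan's own precision figures.** Half-width = 1.96 × √(p(1−p)/n).

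- p = 0.50: n = 100 gives 9.8 points and n = 250 gives 6.2, as stated in section 7.5.1. All 20 cells of Table 13 reproduce to rounding.
- p = 0.70: 9.0 and 5.7 points, also as in Table 13.

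**3. Pass mark.** Table 7 lists 12 HCP and 13 user knowledge questions. 0.80 × 12 = 9.6, so 10 correct are needed; 0.80 × 13 = 10.4, so 11 are needed.

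**4. Shift from exposure.** Let p be the true success rate without exposure and f the share of respondents who see the answers first. Neither is in the documents; both are assumptions. If every exposed respondent passes:

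expected rate = p + f(1−p), and the f that gives 70% is (0.70−p)/(1−p).

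- p = 65%: 0.05/0.35 = 14.3%
- p = 60%: 0.10/0.40 = 25%
- p = 55%: 0.15/0.45 = 33.3%

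The exact binomial chance that the observed rate reaches 70%, taking each survey separately, is:

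| p | f | Expected rate | n = 100 (at least 70) | n = 250 (at least 175) |
|---|---|---|---|---|
| 65% | 0 | 65.0% | 0.173 | 0.055 |
| 65% | 10% | 68.5% | 0.420 | 0.332 |
| 65% | 20% | 72.0% | 0.715 | 0.782 |
| 60% | 0 | 60.0% | 0.025 | 0.001 |
| 60% | 20% | 68.0% | 0.378 | 0.273 |
| 60% | 30% | 72.0% | 0.715 | 0.782 |
| 55% | 0 | 55.0% | 0.002 | 0.000 |
| 55% | 20% | 64.0% | 0.125 | 0.027 |
| 55% | 30% | 68.5% | 0.420 | 0.332 |

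If only 90% of exposed respondents pass, p = 65% and f = 20% give 0.8 × 0.65 + 0.2 × 0.90 = 70.0%, with chances of 0.549 and 0.531.

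**5. Would the data show it?** At p = 65% and f = 10% the shift is 3.5 points, smaller than either half-width at 70%. An early-versus-late split is weak too. With equal halves near 70%, the 95% half-width of the difference is 1.96 × √(2 × 0.21/125) = 11.4 points for users and 1.96 × √(2 × 0.21/50) = 18.0 points for HCPs.

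**The case against.** The strongest reply is that the PDF may add little. Section 7.9 already concedes that the answers can be found in the aRMMs, which are online, and the survey can be saved and resumed. Anyone determined to look things up needs no other respondent's PDF. Payment is for completion and not for score, so no incentive to obtain the answers is shown. Immediate feedback is a deliberate educational choice, and it contradicts nothing else in the protocol. This stands as far as size is concerned: the added effect is unknown and may be small. It does not remove the route, which is avoidable.

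The illustrative true rates also lie below the cut-off, where a shift matters most. The protocol expects the 70% target to be met, and if the true rate is at or above 70%, a pass is not a false one. This stands too.

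A reader might infer more than the documents support:

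- That the result *is* biased. No exposed share is given.
- That every respondent receives a portable answer list. The text says the answers are displayed, where applicable. It does not say whether the PDF can be saved, and no PDF is described for the paper survey (section 7.6).
- That respondents share clinics. Section 7.5.1 mentions several respondents from one practice only as a possibility, and both groups may come through a vendor.
- That a referring HCP hands users their answers. The two surveys have different questions (Table 7), so that path is indirect at most.
- That the whole success assessment is affected. The argument reaches the knowledge score only.

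Parts of sections 7.7.2 and 7.9 are redacted, so it cannot be confirmed that no related analysis or limitation exists there.

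**Conclusion.** The point holds as a design risk, not as a demonstrated bias. The protocol releases the correct answers to online respondents while the same survey is open, and no visible safeguard is directed at their reaching later respondents. Any effect on the knowledge success rate would be upward.

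Its size cannot be derived from the documents. Under the assumption most favourable to the concern (every exposed respondent passes), roughly one respondent in seven would have to be exposed to lift a true 65% to the cut-off, one in four to lift 60%, and one in three to lift 55%. No stated sample size or precision figure changes. The change is worth making because it is cheap and removes the route.

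**What to change.** In section 7.5.2, show only the aRMM link after submission, and email the item-level answer PDF to respondents once recruitment for that survey has closed. Email addresses are already collected at screening and consent. The PDF can be the same general list of correct answers for everyone, so it need not be tied to anyone's responses.

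Two optional additions:

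- List the risk in section 7.9.
- Report the knowledge pass rate by early versus late completion, as a descriptive check only. Recruitment may expand by region and be retargeted while the survey is open, so a trend could not be attributed to circulated answers, and step 5 of the working shows how imprecise the comparison would be. A breakdown by clinic or referral source is not available as planned, because Tables 2 and 3 list no such identifier.

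Cost: one survey-programming change, one mailing per survey and, if wanted, one table. The real downside is that item-level feedback reaches early respondents up to about five months later. The aRMMs are still offered at once, which keeps most of the educational purpose.

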## 7.6. Data Management

For the primary objectives, this study will include data collection through cross-sectional HCP and user surveys.

For the secondary objectives, this study will include data collection through cross-sectional HCP and CAB-LA user surveys, as well as a retrospective analysis of the Aprelude Supports Program.

The HCP and user surveys will be available as a secure custom online survey, that will be compatible with mobile phones and computer platforms. Additionally, the user survey will be available as a paper option for users to complete at participating clinical study sites, as needed.

## 7.7. Data Analysis

The analysis for the study will primarily be descriptive and will be guided by the statistical analysis plan and shell results tables for the study. To analyze and synthesize study data, in general, binary and categorical outcomes, endpoints will be presented as numbers (N) and percentages (%). Continuous endpoints will be presented using mean, standard deviation (SD), median, interquartile range (IQR), 95% CIs, minimum, and maximum values.

Results will be reported overall and by characteristics of interest (i.e., for HCP survey, by HCP type [e.g. physician, nurse, pharmacist]; for user survey, the location of practice where they receive CAB-LA (institution vs. community]).

All analyses will be performed in R (R Foundation for Statistical Computing, Austria). Additional publicly available packages used may include tidyverse for data cleaning and manipulation, openxlsx for reading and exporting Microsoft Excel files, ggplot2 for creating data visualizations, stringr for manipulating text data, and officer and rvg to print R outputs to Microsoft Word or Microsoft Powerpoint.

#{vault:document\_date\_\_v}

Protocol for Non-Interventional Studies PASS Studies and Non-PASS Studies (4.0) March 2024

Template Doc ID: TMF-15706807

Parent Doc ID: VQD-SOP-066694

To ensure robustness of study findings, a sensitivity analysis will be conducted, if necessary, to exclude data collected from individuals who are deemed to have contributed poor quality responses. Specifically, participants may be flagged for exclusion if they provide inconsistent responses to a question repeated within the survey to test consistency, and/or if their total survey completion time falls below a threshold that suggests insufficient engagement with the survey. The threshold will be determined based on the distribution of completion times in the study sample and in consultation with the GSK team (the estimated total completion time is 30 minutes for the HCP survey [14 minutes for the primary objective questions] and 35 minutes for the user survey [13 minutes for the primary objective questions]). The sensitivity analysis will compare results with and without exclusion of flagged participants to evaluate the potential impact of poor-quality data on the findings of the study.

### **7.7.1. Primary Analysis**

#### **7.7.1.1. Main Analytical Approach**

##### **Primary Objectives**

The characteristics of HCPs and CAB-LA users will be summarized as frequencies and percentages (categorical variables) or as means, SD, medians and IQR (continuous variables). These will be summarized overall, by characteristics of interest (i.e., for HCP survey, by HCP type [e.g. physician, nurse, pharmacist]; for user survey, whether a user is a naïve or experienced with PrEP use, the location of practice where they receive CAB-LA (institution vs. community)) will be included in the stratified analyses.

The cross-sectional survey questions – addressing HCP and CAB-LA user knowledge, attitudes, and behaviours – will largely have categorical response options and will also be summarized as frequencies and percentages. By design, most survey data collected will be categorical. The proportion of correct and appropriate answers to key survey questions will be summarized, among those HCPs and CAB-LA users who provided responses to those questions (missing data will be summarized but not counted as a denominator in the proportions). The number and percentage of HCPs and CAB-LA users who have provided correct responses to knowledge questions will be summarized for each question, as well as the number and percentage of HCPs and CAB-LA users who have provided correct responses to at least 80% of all questions (target threshold for the study based on previous studies). Similarly, the number and percentage of HCPs and CAB-LA used who have provided responses indicative of optimal behaviour will be summarized for each question. Specific behaviours will be identified where less than 80% (or alternative thresholds) of participants reported optimal behaviour. Results will be presented overall for HCPs and CAB-LA users, as well as stratified by characteristics of interest (see section 7.7.2 for details). Free-text response options will be summarized for specific questions.

In addition to numeric results tables, customized visualizations will be developed to convey survey results for HCPs and CAB-LA users. These will include various histograms or bar charts to display the distribution of HCP and CAB-LA user responses for key survey items.

The participation rate (i.e., the proportion of participants completing the survey among those who consented to participate) for the HCP and CAB-LA user surveys will be assessed, as well as the level of completion of surveys and missing data among those who participated in the survey study. In cases where a significant amount of missing data is observed, we will conduct a comparative analysis between participants who completed the survey and those who did not, to determine if systematic differences exist between these groups. This analysis will help guide our strategy for addressing missing data, which may include sensitivity analyses to minimize potential biases in our findings.

## Secondary Objectives

For both the survey and the retrospective cohort analysis, the characteristics of HCPs and CAB-LA users will be summarized as frequencies and percentages (categorical variables) or as means, SD, medians and IQR (continuous variables). These will be summarized overall and by characteristics of interest (see section 7.7.2 for details).

The survey questions will largely have categorical response options, which will be summarized as frequencies and percentages. The analysis will be guided by shell tables developed based on the final version of the survey. Results will be presented overall for HCPs and CAB-LA users, as well as stratified by characteristics of interest (see section 7.7.2 for details). The participation rate for the HCP and CAB-LA user surveys will be assessed, as well as the level of completion of surveys and missing data among those who participated in the survey study.

The retrospective cohort analysis used to understand utilization patterns will be summarized as frequencies and percentages (categorical variables) or medians and IQR (for continuous variables). The analysis will be guided by shell tables developed based on data available through the Apertude Supports Program. Results will be presented overall for CAB-LA users and stratified by characteristics of interest (see section 7.7.2 for details).

In addition to numeric results tables, customized visualizations will be developed to convey survey results for HCPs and CAB-LA users, and retrospective cohort analysis results for CAB-LA users. These will include various histograms or bar charts to display the distribution of HCP and CAB-LA user responses for key survey items and key utilization metrics.

The participation rate for the HCP and CAB-LA user surveys will be assessed, as well as the level of completion of surveys and missing data among those who participated in the survey study.

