#### Secondary Objectives

For the secondary objectives 1 through 8, primary data will be collected through surveys administered to HCPs and CAB-LA users (see Table 1). The HCP and user surveys will be conducted at one time point corresponding to approximately 18-months +/- 2-month post CAB-LA launch (December 2025 to April 2026).

For secondary objectives 6 and 9 a retrospective cohort analysis will be executed using data from the CAB-LA patient support program (“Apretude Supports Program”) database (Table 1), which captures basic CAB-LA use information for all individuals enrolled in the program. In the Apretude Supports Program database, data will be included for individuals initiating CAB-LA between 15 July 2024 (the date of commercial availability in Canada) and October 2026 (the ascertainment period). Within this ascertainment period, eligible individuals will be indexed into the cohort at the date of initiation of CAB-LA injections. An ascertainment period end date of October 2026 was chosen to allow for a minimum 1-year follow-up from initiation of CAB-LA (index date) given final analysis will take place November 2027. An interim analysis is planned for Q1/Q2 2026 for data available up to that time point (July 2024 to Q1/Q2 2026).

Two separate sources of CAB-LA user demographic data will be available in this study to address secondary objective 6: one from the CAB-LA user survey and one from the Apretude Supports Program database. If linkage between the survey data and PSP database is feasible, the analysis will aim to combine the data to gain further insights particularly in regards to user factors impacting utilization patterns. The CAB-LA user survey data will be used to explore relationships between demographic characteristics and objectives 7 and 8, while the Apretude Supports Program data will inform analyses related to objective 9.

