## **7.3. Variables**

### **7.3.1. Exposure Definitions**

#### *HCP Survey*

For HCPs, exposure will be defined as having prescribed or managed use of CAB-LA for the prevention of HIV-1 among individuals at high risk in Canada eligible for CAB-LA based on the HC indication.

*User Survey*

For CAB-LA users, exposure will be defined as having previously initiated CAB-LA for the prevention of HIV-1. In the survey, this is defined as having received at least one dose of CAB-LA at the time of survey enrolment.

*Apretude Supports Program Database Analysis*

For CAB-LA users, exposure will be defined as having initiated CAB-LA for the prevention of HIV-1. In the Apretude Supports Program database analysis, this is defined as enrollment and initiation of CAB-LA through the Apretude Supports Program within the ascertainment period (i.e., have received at least one injection of CAB-LA, with the first dose taking place between July 2024 and October 2026). Data will be included for users until the end of the follow-up period (October 2027) or until discontinuation.

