**Table 12. Outcome assessed for secondary objective #9**

Category	Sub-category	Details
Utilization patterns	• Use of oral lead-in	
 
▪ Frequency of use
 
▪ Duration of use
 

	• Use of oral bridging	
	• Adherence to CAB-LA	
 
▪ Measured as proportion of days covered (PDC)                             
 
○ Ratio of number of days the user is covered by the medication during a specific period to the total number of days within that period                                     
 
• Measured on user’s coverage (days supplied) with CAB-LA
 
 
 
 
 

Category	Sub-category	Details
		
 
Based on available follow-up time within the Apretude Supports Program database
 

	
 
Timing of injections (relative to labeled dosing schedule)
 
	
 
Early, on-time, late (with 7-day grace period)
 

	
 
Gaps in therapy
 
	
 
Missed injections (relative to labeled dosing schedule), reasons for missed injections
 
Missed injections being planned or unplanned
 
Use of oral bridging, planned or unplanned                             
 
Type and frequency of oral bridging agents used
 
Duration of oral bridging
 
 
 

	
 
Persistence on CAB-LA
 
	
 
Time to discontinuation
 
% of users who remain on drug, and are still at risk of HIV infection, at end of follow-up (will depend on data availability for at-risk status, either through PSP variables or through linkage with survey data)
 

	
 
Discontinuation
 
	
 
Rates of discontinuation
 
Reasons for discontinuation
 

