Status Date Discontinued	The date on which the patient was identified as discontinued or opted out of the APRETUDE SUPPORTS PROGRAM.
Status Reason Discontinued	Reason the patient stopped APRETUDE therapy or left the APRETUDE SUPPORTS PROGRAM.
Missed Injection Status	Description of the patient's status following missed injection (HCP contacted, Oral bridging initiated, oral bridging completed)
Incomplete Reason	Reason the patient did not receive injection. Accompanies an 'incomplete' Injection Status only

#{vault:document\_date\_\_v}

Protocol for Non-Interventional Studies PASS Studies and Non-PASS Studies (4.0) March 2024

Template Doc ID: TMF-15706807

Parent Doc ID: VQD-SOP-066694

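### Programme-database persistence is a percentage on drug at an end of follow-up that varies by user, and the protocol states neither how users still on drug enter time to discontinuation nor how programme leavers are classified

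*Protocol*

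**What the plan says.** Table 12 of the protocol lists the outcomes for secondary objective 9. Persistence has two parts: "Time to discontinuation", and the percentage "of users who remain on drug, and are still at risk of HIV infection, at end of follow-up". The at-risk part depends on data availability. Discontinuation is listed separately as "Rates of discontinuation", with no denominator given.

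Section 7.7.1.1 (Secondary Objectives) gives the summary rule for these data: "utilization patterns will be summarized as frequencies and percentages (categorical variables) or medians and IQR (for continuous variables". The synopsis repeats it. Section 7.7 refers the analysis to a statistical analysis plan and shell tables that are not at hand, and part of section 7.7.2 is redacted.

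On timing, section 7.1 takes in "individuals initiating CAB-LA between 15 July 2024 (the date of commercial availability in Canada) and October 2026 (the ascertainment period", with the end date "chosen to allow for a minimum 1-year follow-up from initiation of CAB-LA (index date". Section 7.3.1 adds: "Data will be included for users until the end of the follow-up period (October 2027) or until discontinuation". An interim analysis is planned for Q1/Q2 2026.

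Annex 1 describes the discontinuation date field as "The date on which the patient was identified as discontinued or opted out of the APRETUDE SUPPORTS PROGRAM". The reason field likewise covers both stopping the drug and leaving the programme. Patient status has three values: on drug, suspended and discharged.

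**The concern.** Entry is staggered over more than two years and there is one calendar cut-off, so each user has a different length of potential follow-up. A percentage on drug at the end of such follow-up averages persistence over whatever durations accrual happens to produce. It has no stated time point, and it changes between the interim and the final analysis even if users' behaviour does not.

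Time to discontinuation is unknown for users still on drug at the cut-off. An ordinary median and IQR has to leave these users out or treat their follow-up time as the event time. Either choice shortens the apparent time on drug.

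The programme fields raise a further question. Sections 7.2.3 and 7.9 recognise CAB-LA use outside the programme, so a person who leaves the programme may still be receiving injections. No rule in the protocol says how such a person is classified.

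The interim results are intended for a conference abstract and the final ones for a report and manuscript. Section 5.2 says that utilization patterns may help inform decisions about population coverage. A fall in the percentage from interim to final could be read as worsening persistence when only follow-up has lengthened.

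**Working it through.** **Follow-up from the protocol's dates.** The last entrants (October 2026) followed to October 2027 have 12 months, or 11 to 13 depending on the days chosen. This reproduces the stated one-year minimum. The first entrants (15 July 2024) have 38.5 to 39.5 months. At the interim, the first entrants have 17.6 months (1 January 2026) to 23.5 months (30 June 2026). The newest have close to zero, because the one-year minimum applies only to the final analysis.

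**Assumptions.** The documents give no persistence figure, exit rate or accrual pattern. The check assumes:
- 12-month persistence S of 60, 70, 80 or 90%;
- a constant hazard λ = −ln(S)/12 per month;
- potential follow-up uniform on 12 to 39 months (final) or 0 to 22 months (interim);
- no loss of at-risk status.

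**Percentage on drug at end of follow-up.** For follow-up uniform on (a, b):

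P = (e^(−λa) − e^(−λb)) / (λ(b − a)).

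For S = 70%, λ = 0.02972:
- final: (0.7000 − 0.3137) / (0.02972 × 27) = 48.1%;
- interim: (1 − 0.5200) / (0.02972 × 22) = 73.4%.

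**Median among discontinuers (final).** Everyone has at least 12 months of potential follow-up, so for m ≤ 12 the median solves 1 − e^(−λm) = ½(1 − P). For S = 70%, 1 − e^(−λm) = 0.2594 and m = 10.1 months. The true median is ln 2/λ = 23.3 months.

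| Assumed 12-month persistence | 60% | 70% | 80% | 90% |
|---|---|---|---|---|
| On drug at end, final (%) | 35.7 | 48.1 | 62.9 | 80.1 |
| On drug at end, interim (%) | 64.9 | 73.4 | 82.1 | 90.9 |
| Interim minus final (points) | 29.3 | 25.3 | 19.2 | 10.8 |
| True median (months) | 16.3 | 23.3 | 37.3 | 78.9 |
| Median among discontinuers, final | 9.1 | 10.1 | 11.0 | 11.9 |
| Median of all observed times, final (simulation) | 14.2 | 16.8 | 19.6 | 22.5 |

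A simulation of 900,000 users per scenario agrees with the closed forms within 0.1 point or month. In it, Kaplan-Meier recovers 12-month persistence within 0.1 point at both analyses. It also recovers the true median within 0.1 month wherever the curve reaches 50%. At 90% persistence the median is correctly reported as not reached.

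**Programme leavers.** Suppose a fraction q per year leave while still on drug and are counted as discontinued. Apparent 12-month persistence is then S(1 − q). For S = 80% and q = 5, 10 or 20%:
- 0.80 × 0.95 = 76%;
- 0.80 × 0.90 = 72%;
- 0.80 × 0.80 = 64%.

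Over the whole grid the loss is 3 points (60% × 5%) to 18 points (90% × 20%). At S = 80% and q = 10%, the discontinuation rate rises from 22.3 to 32.9 per 100 person-years. Censoring leavers restores 80% and 22.3 if leaving is unrelated to later discontinuation.

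**The case against.** A reader might infer that the protocol analyses these data without censoring and that objective 9 will therefore be biased. The text does not support that. Nowhere does it say that users still on drug are dropped or counted as events. A median and IQR can be Kaplan-Meier quantiles, and discontinuation rates can be per person-time. Section 7.3.1 already supplies an end date. The estimator may be in the statistical analysis plan or in the redacted part of section 7.7.2. Its absence from the protocol is no fault in itself.

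A reader might also infer that most times will be censored. At the final analysis this depends on the rate: 36% at the low end of the assumed range and 80% at the high end.

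Nor does Annex 1 count every programme exit as stopping CAB-LA. It describes vendor fields, and the reason field, which is extracted, may separate the two.

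The end-of-follow-up percentage and 12-month persistence are different quantities, so a gap between them is not bias in the first. The calculation also omits the at-risk condition in Table 12. A constant at-risk share would scale the interim and final percentages alike and leave their ratio unchanged; how the share changes over time is unknown. Finally, no interim-to-final comparison is planned.

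All of this stands. What remains is that the end-of-follow-up percentage is a stated definition in Table 12, not an omission. An analysis plan that follows it literally inherits its dependence on accrual.

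**Conclusion.** The point holds as an inexpensive improvement to secondary objective 9. As defined, the persistence percentage has no fixed time point. Under one constant hazard it would differ between interim and final by about 11 to 29 points over the assumed range. If the median and IQR are computed plainly among discontinuers, the median would be about 9 to 12 months whatever the true value between 16 and 79, and so would say little about persistence. Persistence may be understated, by 3 to 18 points at 12 months for assumed exit rates of 5-20% per year, if leavers are counted as stops.

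These sizes rest on assumed rates, constant hazards and uniform accrual. The last two effects also depend on choices that the protocol leaves open. Objective 9 is descriptive and not mandated by the regulator. The primary knowledge, attitude and behaviour objectives are untouched.

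**What to change.** In Table 12 and section 7.7.1.1:

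1. Report Kaplan-Meier persistence from first injection at a fixed time, at least 12 months, with 95% CI, at both the interim and the final analysis. It can replace the end-of-follow-up percentage or stand beside it.
2. Take the median and IQR of time to discontinuation from the Kaplan-Meier curve, censoring at the data cut-off, and report a quantile as not reached where that applies.
3. Define discontinuation as stopping CAB-LA, using the Status Reason Discontinued field. Censor programme exits without a drug stop, and add a sensitivity analysis that counts them as discontinuations.

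The cost is wording and standard survival code in R, the software already planned. The first-dose date and the discontinuation date and reason are already to be extracted. Two limits should be stated: censoring leavers assumes that exit is non-informative, and the third step works only as far as the recorded reasons separate the two kinds of exit. If the analysis plan already contains these rules, aligning Table 12 with it is enough.
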